## MEDICAL PROTOCOL (HRP-590)

PROTOCOL TITLE: Effect of mechanical intervention on the scalp microbiome: setting the stage for the future management of cicatricial alopecias

VERSION DATE: 05 August 2023

In OnCore (oncore.umn.edu)

Store       Analyze       Share

In the University's Box Secure Storage (box.umn.edu)

Store       Analyze       Share

In an AHC-IS supported server. Provide folder path, location of server and IT Support Contact:

Store       Analyze       Share

In an AHC-IS supported desktop or laptop. Provide UMN device numbers of all devices:

Store       Analyze       Share

Other. Describe:

Indicate if data will be collected, downloaded, accessed, shared or stored using a server, desktop, laptop, external drive or mobile device (including a tablet computer such as an iPad or a smartform (iPhone or Android devices) that you have not already identified in the preceding questions

I will use a server not previously listed to collect/download research data

I will use a desktop or laptop not previously listed

I will use an external hard drive or USB drive ("flash" or "thumb" drives) not previously listed

I will use a mobile device such as an tablet or smartphone not previously listed

16.8 Consultants. Vendors. Third Parties: N/A

16.9 Links to identifiable data: All data will be identified with an identification code unique to the participant. Study staff will keep the mapping of identification code to the identity of the participant on an encrypted password protected computer stored separately from the data in the University's Box Secure Storage. That same identification code will be used for data-entry into the REDCap database. Any internal data reports will use only these codes and will not use any identifiable information. Any external data reports, abstracts, publications, presentations, etc. will present de-identified, grouped, and/or aggregate data. Any reports to the University of Minnesota IRB (such as Adverse Event reporting and annual renewal reports) will be kept confidential; they will not include participant- identifiable information; only the participant's identification code will be used.

## MEDICAL PROTOCOL (HRP-590)

PROTOCOL TITLE: Effect of mechanical intervention on the scalp microbiome: setting the stage for the future management of cicatricial alopecias

VERSION DATE: 05 August 2023

*16.10 Sharing of Data with Research Team Members:* Only IRB-approved members of the study team will have access to the data. Data will be shared through REDCap or the University's Box Secure Storage.

*16.11 Storage and Disposal of Paper Documents:* This study will not require the use of paper documents. All documents will be stored electronically via the REDCap database or the University's Box Secure Storage. Consent forms will be signed and stored in REDCap.

## 17.0 Confidentiality

*17.1 Data Security:* Only research staff will have access to subject information. All participant data will be stored in locked cabinets and electronically in REDCap. Passwords will be required to access data in REDCap. Study data will be available only to select staff that need access to the information to conduct their research duties. To minimize the volume of documents containing identifying information, all study documents or data will contain a unique participant ID that will be used when possible. No copy of the consent form or other research study information will be placed in the participant's medical, employment, or educational records.

## 18.0 Provisions to Monitor the Data to Ensure the Safety of Participants

### 18.1 Data Integrity Monitoring:

Independent monitoring of the clinical study for clinical protocol and IND/IDE application compliance will be conducted by the University of Minnesota's Clinical and Translational Science Institute (CTSI) clinical trial monitoring service. The CTSI monitors will confirm that study activities are in compliance with the approved protocol and applicable regulatory authorities (FDA, IRB, local and State regulations). Frequency of monitoring visits will occur after IRB approval and as soon as possible after the first subject is enrolled, during the study data collection phase and after the last subject has completed his/her participation in the study. Monitoring visits will be performed annually, at a minimum. This monitoring schedule may be revised based on the following considerations:

- Accrual rate
- Protocol deviations or non-compliance with regulatory authorities
- Magnitude of data corrections required
- Study stage (e.g. start-up or follow-up)
- Complexity of the trial
- Request (IRB, Investigator, other etc.)

The sponsor-investigator will permit direct access to the study monitors and appropriate regulatory authorities to the study data and to the corresponding source data and documents to verify the accuracy of these data.

## MEDICAL PROTOCOL (HRP-590)

PROTOCOL TITLE: Effect of mechanical intervention on the scalp microbiome: setting the stage for the future management of cicatricial alopecias

VERSION DATE: 05 August 2023

Primary responsibilities of the monitors will include verifying the following:

- Investigator qualifications
- Facilities and equipment
- Storage, dispensing and disposition of investigational products
- Protocol compliance
- Informed consent
- Training and delegation of authority
- Subject eligibility
- Recruitment, screening and enrollment
- Verification of data and data clarification
- Adverse event reporting
- FDA correspondence
- Deviations

### 18.2 Data Safety Monitoring:

The investigators will ask participants about adverse events at each of the follow-up study visits. Participants are encouraged to call in if they experience any adverse events prior to that time. Study progress and safety will be reviewed monthly (and more frequently if needed) by the PI. The PI will review patient safety data monthly and determine if adverse event rates are consistent with pre-study assumptions, or if there is an increased rate of risk or new information that should be shared with enrolled participants. If a serious adverse event (SAE), Unanticipated Problem Involving Risks to Subjects or Others (UPIRTSO), or other event causing risk to the research subjects occurs, the clinical research team will notify the PI immediately. The PI will assure the study is conducted in accordance with the investigator's agreement, the investigational plan, the IDE and other applicable FDA regulations, and conditions of approval imposed by the reviewing IRB.

All AEs will be assessed by the study investigators using a protocol defined grading system.

- Mild – Events require minimal or no treatment and do not interfere with the participant's daily activities.
- Moderate – Events result in a low level of inconvenience or concern with the therapeutic measures. Moderate events may cause some interference with functioning.
- Serious – Events interrupt a participant's usual daily activity and may require systemic drug therapy or other treatment. Severe events are usually potentially life-threatening or incapacitating.
- Related – The AE is known to occur with the study intervention, there is a reasonable possibility that the study intervention caused the AE, or

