### 5.2 Study Procedures:

## MEDICAL PROTOCOL (HRP-590)

PROTOCOL TITLE: Effect of mechanical intervention on the scalp microbiome: setting the stage for the future management of cicatricial alopecias

[figure not shown]
VERSION DATE: 05 August 2023

Subjects will come for Venus Glow™ treatments, two treatments over a two week period. At the first visit they will complete an initial questionnaire regarding current scalp care practices, skin type, and hair type. An initial baseline scalp swab and HairMetrix photography in the two swab sites will be taken at the beginning of this visit. Treatment with the Venus Glow™ device will also occur. To treat, the scalp will be divided into four quadrants. In the right two quadrants, the hair will be sectioned into both vertical and horizontal parts about 1 cm apart. The tip of the device will then be dragged in zig zag movements along vertical part widths, then along horizontal part widths, and then once more along the vertical part widths, to account for a total of three passes. The left side will not be treated with the device.

Swab samples will be collected from the untreated right mid-frontal scalp, treated right mid-frontal scalp, and the untreated left mid-frontal scalp and will be collected at the first baseline and concurrent treatment session, second treatment session and 3-6 days after the last treatment when participants have returned to their usual cleansing routine. In addition, HairMetrix photography will be taken in the two swab sites (right scalp swab site and left scalp swab site) before treatment at the first baseline and concurrent treatment session, the second treatment session and the follow-up session 3-6 days after the last treatment.

All swabs will be taken 10 cm from the nasal bridge and 3 cm from the midline (see Photo 1 below). Subjects will avoid shampooing, chemical, or heat treatments, but will be able to wet their hair during the study.

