### Photo 1: Swab Sites (25)

**MEDICAL PROTOCOL (HRP-590)**

PROTOCOL TITLE: Effect of mechanical intervention on the scalp microbiome: setting the stage for the future management of cicatricial alopecias

VERSION DATE: 05 August 2023

To collect samples, sterile cotton swabs will be soaked for at least 30s in collection buffer (0.15 M NaCl, 0.1% Tween-20) and rubbed on the scalp surface in the following locations: right and left mid-frontal scalp, covering an area of 4 cm^2 per scalp section. Swabs will be stored in a collection buffer amended to a final concentration of 10% glycerol and stored at -80 °C prior to shipping/processing. If necessary, samples will be shipped to the microbiology lab on dry ice. Control swabs exposed to just room air and the buffer will be collected throughout the course of the study when treating participants. DNA will be extracted from the swab tips using the Daisy PowerSoil Pro DNA isolation kit (QIAGEN). Bacteria/archaea will be characterized by amplification and sequencing using the 515F/806R primer set targeting the V4 hypervariable region of the 16S rRNA gene. Fungal communities will be characterized by sequencing of the ITS1 region using the ITS1f/ITS2 primer set. Paired-end sequencing will be carried out at a read length of 300 bp on the Illumina MiSeq platform by the UMN Genomics Center. Bioinformatics and computational analyses of microbiome data will be done by the [name] lab using mothur software and raw data will be made publicly available on the Sequence Read Archive.

5.3 Study Duration: The total duration of participant participation will be approximately 2.5 weeks. The duration anticipated to enroll all study participants is expected to be approximately 5 months. It is anticipated that it will take just over 1 years to complete all study procedures including data analysis.

|  |   |
|--|---|

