## MEDICAL PROTOCOL (HRP-590)

PROTOCOL TITLE: Effect of mechanical intervention on the scalp microbiome: setting the stage for the future management of cicatricial alopecias

VERSION DATE: 05 August 2023

|  |   |
|--|---|
|  | 

• Swab of right and left mid-frontal scalp prior to treatment

• HairMetrix photography before treatment

• Right side of scalp treatment with the Venus Glow™ device and brush (left side will not be treated)

• Swab of right mid-frontal scalp post- treatment

   |
| Beginning of Week 1 - Second Treatment
(+/- 3 days) | 

• Participant report of adverse events

• Swab of right and left mid-frontal scalp prior to treatment

• HairMetrix photography before treatment

• Right side of scalp treatment with the Venus Glow™ device and brush (left side will not be treated)

• Swab of right mid-frontal scalp post-treatment

 |
| End of Week 1- Final Visit (+/3 days)                   | 

• Participant report of adverse events

• Swab of right and left mid-frontal scalp

• HairMetrix photography

  |

All participants will have a final 3-6 day visit and swab collection after their treatments have been completed and they have returned to their typical hair and scalp care routine, described above. All visits including this final visit will be compensated at \$10 per visit. If a patient happens to miss a study visit, one of the study staff will reach out to the patient via a phone call.

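### Minor: a brief adverse-event check after treatment at both treatment visits would prompt for symptoms that are now asked about only at the next visit, days later

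*Combined protocol and SAP*

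**What the plan says.** Section 18.2 sets the rule for collecting adverse events: "The investigators will ask participants about adverse events at each of the follow-up study visits". Between visits, participants are invited to telephone.

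The visit table in Section 5.3 puts this into practice as follows.

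- **Week 0, first treatment.** No adverse-event entry. The list ends with "Swab of right mid-frontal scalp post- treatment".
- **Second treatment**, headed "Beginning of Week 1 - Second Treatment", with a window of 3 days either way. The first entry is "Participant report of adverse events". The two-sided swab, the photography, the treatment and the post-treatment swab follow. The swab and the photography are labelled as coming before treatment. The adverse-event entry has no timing label.
- **Final visit.** The same adverse-event entry, again listed first. Section 5.2 places this visit "3-6 days after the last treatment when participants have returned to their usual cleansing routine", and the text below the Section 5.3 table agrees: "All participants will have a final 3-6 day visit and swab collection after their treatments have been completed".

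Section 13.1 names six foreseeable risks: irritation, redness, headache, itching, tingling and abrasion. Section 25.1 has the PI or Co-PI at every treatment, together with research staff.

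**The concern.** The participant is in the room with staff just after each treatment, when the listed reactions seem most likely to be felt. The schedule does not ask about them then. Redness or abrasion can be seen and noted. Headache, itching and tingling cannot, so on the day they are recorded only if the participant mentions them. After that, the record depends on a telephone call or on memory at the next visit.

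What is at stake is the quality of symptom reporting. Section 18.2 has the PI compare adverse-event rates each month with what was assumed beforehand. It also makes frequency one ground for calling an event unexpected, and timing relative to treatment one ground for calling it related. All three rest on how and when events are collected. Prior experience is limited too: Section 2.3 says the device has not been studied on the scalp, and Section 4.1 describes the use as off-label.

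**Working it through.** No sample-size, power or error-rate figure is involved, and the plan states no figure to reproduce. The check compares the schedule with Sections 13.1 and 18.2 and computes the gap from each treatment to the next scheduled question.

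**1. Scheduled questions by visit (Section 5.3 table)**

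| Visit | Treatment given | Adverse-event entry | Position |
|---|---|---|---|
| Week 0 | Yes | None | Not applicable |
| Second treatment | Yes | One | First in list, no timing label |
| Final visit | No | One | First in list |

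The absence at Week 0 is explicit. At the second visit, the reading that the question precedes treatment is an inference: the list otherwise runs in time order, and no adverse-event entry follows the treatment.

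**2. Gap after treatment 1**

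Assume that Week 0 is day 0 and that the beginning of Week 1 is day 7. The documents give no day number.

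- Earliest: 7 − 3 = 4 days.
- Latest: 7 + 3 = 10 days.

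If the nominal day is *d* instead of 7, the range is *d* − 3 to *d* + 3.

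Compatibility check: the latest second treatment (day 10) plus the longest stated follow-up (6 days) is day 16, and 16 / 7 = 2.3 weeks. Section 5.3 says "The total duration of participant participation will be approximately 2.5 weeks", which is 2.5 × 7 = 17.5 days. The assumption fits, though this does not prove it.

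**3. Gap after treatment 2**

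Sections 5.2 and 5.3 both state 3 to 6 days. As a check against the table, take the end of Week 1 as day 13. The nominal gap is then 13 − 7 = 6 days, inside the stated range. Applying the two 3-day windows independently would give 10 − 10 = 0 days at the shortest and 16 − 4 = 12 days at the longest. The stated 3 to 6 days is the specific rule, so it is used here.

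**4. Which listed risks depend on asking (my classification of the Section 13.1 list)**

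- Symptom only: headache, itching, tingling = 3.
- Visible: redness, abrasion = 2.
- Mixed: irritation = 1.
- Total: 3 + 2 + 1 = 6.

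**5. Number of events missed**

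This cannot be computed. The documents give no event rate, no symptom duration and no measure of recall.

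**6. Cost of a check after each treatment**

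One form for each of 2 sessions: 20 × 2 = 40 and 25 × 2 = 50 at the enrolment in Section 5.1. At the 40 participants still stated in Sections 10.1 and 25.1, 40 × 2 = 80.

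**The case against.** The case for leaving the plan alone is substantial.

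- **The plan is consistent.** Section 18.2 promises questions at follow-up visits, and the table has one at the second visit and one at the final visit. No commitment is broken.
- **Each treatment is already followed by an open question.** It is not limited to symptoms present on the day of asking, so a headache or itching from the treatment day falls within it. What remains is recall over several days in healthy adults who can also call in.
- **Same-day oversight is real.** Section 25.1 puts the PI or Co-PI and research staff at every treatment and allows one to two hours of staff time per visit. The case report forms are not in the documents, so whether they already prompt staff cannot be determined.
- **The risk looks low.** The device is Class 1, injection is at its weakest setting and only water is delivered. Suction is at maximum, but the next sentence of Section 4.1 reports that neither sensitivity nor adverse events such as bruising have been seen on the scalp at that setting. Section 25.1 anticipates no severe consequences.
- **There is no benchmark.** Without a stated event rate, no distortion of the PI's monthly comparison can be demonstrated, and a same-day question would not supply the missing rate.

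All of this stands, and it is why the point is minor. It does not remove the narrower observation that the plan says when to ask and does not provide for asking at the end of a treatment session.

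A reader might infer that treatment-day events go uncaptured, or that it is established that nobody asks after treatment 2. The documents support neither. Staff presence, volunteered reports and calls all provide capture, and the second-visit timing rests on list order alone.

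**Conclusion.** This is a minor, inexpensive improvement to safety data collection. The Week 0 visit has no adverse-event entry. At the second visit the single untimed entry appears, by list order, to come before treatment. Treatment-day headache, itching and tingling are therefore prompted only at the next visit: about 4 to 10 days after treatment 1 and 3 to 6 days after treatment 2, unless the participant speaks up or calls.

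The first range assumes that the beginning of Week 1 is day 7. The second is stated in the protocol, but its use here assumes that the second-visit question is asked before treatment.

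A reader might go further and conclude that adverse-event rates will be understated. Some unvolunteered symptoms could be forgotten, but the documents give nothing from which to say how many. The primary result is untouched: Section 3 has no safety endpoint and Section 15.1 has no safety analysis.

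**What to change.** Make two wording changes.

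1. In the Section 5.3 table, after the post-treatment swab at both treatment visits, add: *Brief adverse-event check: staff-observed and participant-reported, with local reactions recorded by treated or untreated side.* Recording the side uses the untreated left scalp as a within-person comparison.
2. Reword the first sentence of Section 18.2 so that the investigators ask after treatment at both treatment visits as well as at each follow-up visit.

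Keep the existing questions at the second and final visits, since they pick up delayed reactions. Labelling the existing second-visit entry as pre-treatment would also remove the ambiguity about its timing.

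The cost is one short form per treatment session, completed by staff already present: 40 to 50 forms at 20 to 25 subjects, or 80 if 40 are treated. The protocol amendment itself is limited to these two places.

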## MEDICAL PROTOCOL (HRP-590)

PROTOCOL TITLE: Effect of mechanical intervention on the scalp microbiome: setting the stage for the future management of cicatricial alopecias

VERSION DATE: 05 August 2023

there is a temporal relationship between the study intervention and event. Reasonable possibility means that there is evidence to suggest a causal relationship between the study intervention and the AE.

- Not Related – There is not a reasonable possibility that the administration of the study intervention caused the event, there is no temporal relationship between the study intervention and event onset, or an alternate etiology has been established.

The Principal Investigator will be responsible for determining whether an adverse event (AE) is expected or unexpected. An AE will be considered unexpected if the nature, severity, or frequency of the event is not consistent with the risk information previously described for the study intervention.

## 19.0 Provisions to Protect the Privacy Interests of Participants

19.1 Protecting Privacy: The study consent form will describe in detail any intrusive, uncomfortable, or unfamiliar questions, procedures, or interactions with researchers or study personnel that the participant will be asked to complete. Furthermore, the study consent form will communicate that it is the participant's right to opt-out of any study procedures for the study or withdraw from the study at any time and this information will be reiterated and revisited periodically throughout the study in advance of intrusive, uncomfortable, or unfamiliar questions, procedures, or interactions. Participants will not be compelled or pressured to provide information or specimens or study data that they do not wish to provide.

19.2 Access to Participants: Participants will be fully informed of the ways in which their data will/may be used during the informed consent process. The research team has been trained in conducting these conversations and the participants are also assessed for their understanding of consent prior to signing the consent form or initiating any study procedures.

## 20.0 Compensation for Research-Related Injury

20.1 Compensation for Research-Related Injury: If this research activity results in an injury, treatment will be available, including first aid, emergency treatment and follow-up care as needed. Care for such injuries will be billed in the ordinary manner, to the participant or his/her insurance company.

20.2 Contract Language: N/A

## 21.0 Consent Process

21.1 Consent Process (when consent will be obtained):

The consent process will take place in a private room at the University of Minnesota Department of Dermatology in the Phillips-Wangensteen building, Maple Grove clinic or the Clinics and Surgery Center. If a patient meets the

## MEDICAL PROTOCOL (HRP-590)

PROTOCOL TITLE: Effect of mechanical intervention on the scalp microbiome: setting the stage for the future management of cicatricial alopecias

VERSION DATE: 05 August 2023

criteria via the phone screening, we will consent the patient at their baseline visit in person. Informed consent is a process that is initiated prior to the individual agreeing to participate in the study and continues throughout the individual's study participation. Extensive discussion of risks and possible benefits of participation will be provided to the participants. REDCap eConsent forms will be approved by the IRB, and the participant will be asked to read and review the document using a tablet provided by the investigator. The investigator will explain the research study to the participant and answer any questions that may arise. All participants will receive a verbal explanation in terms suited to their comprehension of the purposes, procedures, and potential risks of the study and of their rights as research participants. Participants will have the opportunity to carefully review the written consent form and ask questions prior to signing. The participant will be asked to sign the informed consent document or electronically sign using the HIPAA compliant REDCap eConsent, prior to any procedures being done specifically for the study. The participants may withdraw consent at any time throughout the course of the trial. A copy of the informed consent document will be given to the participants for their records. The rights and welfare of the participants will be protected by emphasizing to them that the quality of their medical care will not be adversely affected if they decline to participate in this study.

- 21.2 Waiver or Alteration of Consent Process (when consent will not be obtained): N/A
- 21.3 Waiver of Written/Signed Documentation of Consent (when written/signed consent will not be obtained): We are requesting a waiver of written/signed documentation of consent for the screening portion of this study. A short phone script will be read to the participant before any screening questions are asked. The participant will need to provide verbal consent to answering these screening questions before proceeding. See attached for the screening phone script.
- 21.4 Non-English Speaking Participants: N/A
- 21.5 Participants Who Are Not Yet Adults (infants, children, teenagers under 18 years of age): N/A
- 21.6 Cognitively Impaired Adults, or adults with fluctuating or diminished capacity to consent: N/A
- 21.7 Adults Unable to Consent: N/A

